Study Title: Evaluation of 19-gauge vs 21-gauge EBUS TBNA in assessing thoracic lymphadenopathy

NCT # NCT03657849

Participant Contact Narrative: Evaluation of 19-gauge vs 21-gauge EBUS TBNA in assessing thoracic lymphadenopathy

1. Summary:

Endobronchial ultrasound-guided transbronchial needle aspirate (EBUS-TBNA) is a technique used to take samples of body tissue inside the chest without having to undergo an operation. During this procedure, a special telescope (called a bronchoscope) is inserted through the mouth into the airways. Ultrasound technology allows the doctor to see the structures just outside the airway. By being able to see the structures outside the airway, the doctor is able to safely pass a fine needle through the airway to take samples of abnormal tissue.

EBUS-TBNA is used to take samples of tissue from the mediastinum. The mediastinum is the part of the chest between the lungs, and contains the heart, gullet, windpipe and lymph nodes. This area of the body is usually difficult to access without open surgery, hence the use of EBUS-TBNA. EBUS-TBNA may be used to investigate enlarged lymph nodes. This may be due to tuberculosis, sarcoidosis or cancer.

Currently, smaller 21-gauge and larger 19-gauge needles are used during the EBUS-TBNA procedure at Regions Hospital. The purpose of this study is to find out which needle is better in finding the explanation for the enlarged lymph nodes, minimizing complications and any follow up procedures that may be necessary if we are unable to get enough tissue during the EBUS-TBNA procedure (surgical sampling, radiological sampling, and/or follow-up imaging).

2. Study Aims:

Using the larger 19-gauge needle instead of 21-gauge needle during EBUS TBNA will have higher yield without increasing complications

Primary outcome:

- 19-gauge needle yield vs 21-gauge needle yield (true positive + true negative)/total

Secondary outcome:

- Number of adequate samples by rapid onsite evaluation (ROSE)
- cytology assessment of sample size
- adequacy for molecular testing for lung cancer

H1: 19-gauge needle will have at least 7% higher absolute yield than 21-gauge needle (current yield for 21-g needle is 83%)

3. Background, Rationale, Significance:

Endobronchial ultrasound (EBUS) transbronchial needle aspiration (TBNA) is regarded as the preferred initial sampling method in assessment of mediastinal and hilar lymph adenopathy [1]. There are several needle sizes available commercially (25-, 22-, 21-, or 19-gauge). The size of the needle may affect the

quantity of tissue obtained, degree of tissue trauma, and amount of aspirated blood; each of which can affect the diagnostic yield.

The 2016 CHEST guidelines [2], recommended the use of either 21- or 22-gauge needle during EBUS TBNA due to similar performance in the published literature but were unable to comment on other needle sizes due to lack of data. Since then few retrospective publications evaluated the recently available 19-gauge needle [3-8]. Biswas et al. repeated EBUS TBNA using 19-G needle in addition to 21-G needle for those patients with an initial negative 21-G EBUS TBNA but have high suspicion for sarcoidosis. The 19-G needle identified granulomas in all 11 patients compared to only 2 in the 21-G needle [4]. All these publications showed similar safety to smaller needles without increased bleeding risk.

One of the drawbacks of EBUS TBNA is the loss of the histological structure due to smaller needle size, leading to lower yield in diagnoses that require preserving the cell structure to make the diagnosis, such as lymphomas (yield 68%) and sarcoidosis (yield 78%) compared to malignancy (yield 90%) [2, 9].

When EBUS does not yield diagnosis, or doesn't provide adequate tissue for molecular testing, patients are usually subjected to further diagnostic testing including repeat imaging studies, and commonly proceeding with more invasive procedures or surgical operations to obtain tissue, which in addition to delaying the diagnosis, causes significant distress for the patients and increase the cost.

We believe that using 19-G needle during EBUS TBNA will improve the diagnostic yield overall and lead to more rapid diagnosis with fewer procedures for the patients which would improve patient's satisfaction and decrease overall cost. The use of a 19-G needle could also result ultimately in fewer total passes which would typically result in less time under sedation for the patient.

4. Approach:

a. Study design:

This is a prospective, diagnostic accuracy study. For each lymph node sampled, we will alternate between the 19-g and the 21-g with each pass. Typically, an average of 5 passes is done in each lymph node (though number ranges from 3-12 based on physician judgment), for the study a minimum of 3 passes with each needle will be requested to provide adequate tissue for comparison. The choice of needle for the first pass will be randomized. More passes will be allowed with alternating needles based clinicians' judgment. Tissue obtained with the 19-g needles will be compared to tissue obtained with the 21-g needles with regards to diagnosis yield and adequacy for molecular testing.

b. Population:

i. Inclusion/Exclusion criteria

Inclusion:

- Age 18 years or older
- Able to provide informed consent
- Referred for EBUS TBNA sampling at Regions Hospital

Exclusion:

- On therapeutic warfarin, plavix or ticagrelor in the last 5 days

- INR >1.8, platelets <50K (evaluated at enrollment if patient has had them drawn as part of standard of care)
- ii. Sample size:

A total of 50 patients will be enrolled, with an average of 1.7 lymphnodes sampled in each patient. Patients will be a convenience sample of patients referred to have the EBUS-TBNA procedure at Regions Hospital during the study period.
- c. Data collection process
 - i. Process steps for identification of patients or records

All patients referred for EBUS TBNA sampling at Regions Hospital who meet the inclusion/exclusion criteria will be approached to be enrolled. These patients will be identified by one of the study investigators. Of note, the exclusion criteria for INR and platelets will have been drawn and evaluated as part of standard of care only, based on the concern for coagulopathy. These are not required to be drawn for study enrollment. All physicians who perform this procedure at Regions Hospital are listed as investigators on this study.
 - ii. Recruitment

Subjects will be identified based on referral for EBUS TBNA procedure at Regions Hospital by one of the study investigators. Because all physicians who perform the EBUS TBNA procedure at Regions are study investigators, one of the investigators will be aware of every patient referred to have this procedure. Upon becoming aware of a patient referred for this procedure, the study investigator will discuss the procedure with the patient.
 - iii. Consent

After initial discussion of the procedure (standard of care), the investigator will describe the option to participate in the study as part of the procedure. The consent will be provided and reviewed with the patient/family, explaining the study verbally. The patient undergoing the procedure will provide consent for him- or herself and will be given sufficient time to privately review the consent form and discuss potential involvement in the study with any family members or LAR, as applicable. The investigator will again meet with the patient to address any questions and discuss enrollment. If appropriate, the investigator will obtain consent from the patient and begin the study procedures.
 - iv. Data Sources:

Data will be obtained before, during, and after the procedure. Demographic data will be obtained prior to the procedure via EMR. Number of passes with each size needle will be recorded in-person following each procedure. Diagnosis yield and adequacy for molecular testing will be obtained following the procedure, from the investigator performing the procedure and from pathology lab analysis as recorded in the EMR and communicated to the investigator per standard practice for this procedure. Complications will be assessed in-person during the procedure and following the procedure via review of the patient's EMR 24± hours after the procedure.
- d. Interventions, treatments

The EBUS-TBNA procedure is done with both 19-g and 21-g needles as standard of care. The conduct of the procedure with both needle sizes in a systematic manner with concurrent data collection as described above is specific to the study. This procedure is conducted at Regions Hospital by the listed study investigators. The procedure typically takes between 20 and 90 minutes to complete, during which time the patient is under moderate sedation. During a standard procedure, the physician always performs at least four passes, sometimes more depending on the adequacy of the tissue being obtained. The average is 5.5 passes per lymph node. Participation in the study will likely result in an additional 1 to 2 total passes per patient. The randomization aspect of this study involves randomizing which needle size the physician starts with, with subsequent passes alternating between the two needle sizes. Initial needle size will be randomized using research randomizer. The randomization assignments for each study ID number will be kept in a document accessible by all investigators for use during enrollments. The investigators will not be blinded to the randomization assignment but the subjects will not be informed of which needle size they were assigned to start with.

e. Outcome/endpoint and other variable definitions, and instruments used

| Variable Name | Data Source | Purpose | Measurement Scale |
|--|---------------|-----------|-------------------|
| Ethnicity | EMR | Covariate | Categorical |
| Age and gender | EMR | Covariate | Categorical |
| BMI | EMR | Covariate | Categorical |
| Primary admission diagnosis | EMR | Covariate | Categorical |
| Secondary diagnoses | EMR | Covariate | Categorical |
| Passes with 21-g needle | In-person CRF | Covariate | Continuous |
| Passes with 19-g needle | In-person CRF | Covariate | Continuous |
| Total lymph nodes sampled | In-person CRF | Covariate | Continuous |
| Total sample yield 19-g | In-person CRF | Outcome | Continuous |
| Total sample yield 21-g | In-person CRF | Outcome | Continuous |
| Number of adequate samples by rapid onsite evaluation (ROSE) | In-person CRF | Outcome | Continuous |

| | | | |
|---|-------------------|-----------|-------------|
| Adequacy for molecular testing for lung cancer | In-person CRF | Outcome | Binary |
| Follow-up procedures required | EMR | Outcome | Categorical |
| Complications (hypotension, hypoxia, bleeding, other) | In-person CRF/EMR | Outcome | Categorical |
| Total time sedated for procedure | In-person CRF/EMR | Covariate | Continuous |

f. Statistical analysis plan:

As each needle will be used for every lymph node evaluated, we will assume a paired data structure for analytic strategies. First, demographics and relevant patient factors in the study sample will be summarized using descriptive statistics. Bivariate comparisons (by needle gauge) will be conducted using McNemar tests, paired t-tests, or alternatives appropriate for paired data as dictated by the nature of each variable. If more flexibility is required (e.g., covariates for adjustment, specific correlation structure, random intercepts/slopes for patient clustering), we will specify linear mixed effects regression models to evaluate yield by needle gauge. For secondary aims (complications, etc.) we will employ descriptive analyses – no formal hypotheses will be tested.

g. Power analysis:

Assuming 85 paired samples (50 patients * 1.7 lymph nodes), a one-sided $\alpha=0.05$, and a standard deviation in yield of 10%, we expect 80% power to detect a mean difference of 2.7%. Given our anticipated yields of 83% (21g) and 90% (19g; 7% increase), we expect sufficient power to detect a statistically significant difference in average yield by needle gauge.

h. Strengths and Limitations:

Strengths of the study include:

- All physicians who perform the EBUS-TBNA procedure at Regions Hospital are investigators on this study, therefore we anticipate being able to approach all qualifying patients for enrollment.
- Both needle sizes are currently used as standard of care, based on physician discretion. Use of these needles in the study is not far from the current standard of care and could inform a more standardized methodology for needle size in the future

Limitations of the study include:

- Providers will not be blinded to needle gauge
- Difficult to attribute complications to a single needle gauge, given both will be administered
- As described above, procedural variation depends on physician judgment, which could bias results if judgment is differential with respect to needle gauge and/or yield

5. Setting/Environment/Organizational feasibility

This study will be conducted at Regions Hospital. Subjects will be identified by EBUS providers upon referral for the procedure. A letter of support from [name], Department head of Critical Care Medicine at Regions Hospital, is included with this application. We do not anticipate that the use of both needle sizes during the procedure will significantly affect the resources or personnel utilized during these procedures.

The Critical Care Research Center staff will be responsible for IRB correspondence and data management after collection. Study investigators are very involved with the study and have strong communication with the CCRC staff. The CCRC has conducted numerous studies in collaboration with the Regions Hospital Critical Care Medicine department.

This study fits with the organizational goals at Regions Hospital because it may help to improve patient satisfaction, decrease patient time under anesthesia, and decrease cost of diagnosis for subjects being evaluated with the EBUS TBNA procedure.

Investigator training: All investigators who will be performing the EBUS TBNA procedure are already trained in the conduct of the procedure and are already familiar with the use of both needle sizes. Prior to the start of the study data collection period, the investigators will attend a training meeting during which the specifics of the protocol will be reviewed and any questions discussed. A checklist will be made for use by the investigators during enrollments and investigators will be trained on this checklist and on the data collection instruments. Research staff will remain in close contact with the investigators and have a 24/7 research number where they can contact a research staff member. Investigators will notify CCRC research staff upon completion of enrollments and data collection for each patient. The research staff will collect all enrollment and data collection paperwork from the investigator. Data will be entered on a per-patient basis into an excel spreadsheet on the internal CCRC shared drive. Physical copies of patient study paperwork will be kept in a locked file cabinet in the CCRC, which is a limited access room that requires badge access with specific permission.

6. Risks and Benefits

Risks of EBUS-TBNA procedure

The risks described in this section are related to the EBUS-TBNA procedure, whether done as standard of care or as part of this research study. Bronchoscopy is generally a safe procedure with about 1 in 100 patients reporting a complication. Complications related to the bronchoscopy procedure can be related to sedation for the procedure or directly from the bronchoscope. Complications related to sedation are hypoxia and hypotension, while those related to bronchoscopy are bronchospasm, laryngospasm, nausea, vomiting, bleeding due to scope trauma, abnormal heart rhythm, and fainting. Complications specifically related to EBUS-TBNA are collapse of the lung and bleeding.

An additional risk to subjects is the potential for a breach in patient confidentiality. All study personnel involved in data collection and analysis are trained in GCP, including issues of confidentiality. All study materials will be kept in a locked file cabinet in a badge-access room with limited access and on secure servers, also with limited access. In addition, subjects will be identified in the database by a study number and links to specific identifiers will be kept in a separate secure location. Database files will be maintained on a password protected computer in a secure location and backed up remotely.

Benefits

Subjects may or may not benefit from being in this study. Because of the possibility of getting more tissue with the larger needle, subjects may be able to avoid further testing that may have been necessary if the smaller needle only was used.

We hope the information learned will help other patients undergoing EBUS-TBNA for enlarged lymph nodes in the future.

7. Data Confidentiality and Privacy

All reports and study materials will be identified only by a subject identification number to maintain subject confidentiality. Tissue samples obtained through the procedure will be identified as per standard procedure for Regions Hospital. These tissue samples will not be retained in any way outside of standard protocol and will not be labeled with the subject's study ID number. A master database linking the patient name & MRN will be maintained on a secure, password protected server in the CCRC. The CCRC uses a secure, electronic system that is currently used at Regions Hospital and is approved by IS&T Security. Any paper case report forms will be stored in locked file cabinets in the CCRC. The CCRC is a locked, protected department with limited badge access for security purposes.

8. Timeline

| | |
|---------------------------------------|-------------------------|
| Submission | April 2018 |
| Review and Approval | April-May 2018 |
| Training | May 2018 |
| Data Collection | June 2018-February 2019 |
| Data Analysis | March-April 2019 |
| Manuscript Preparation and Submission | May-June 2019 |

9. Dissemination/Sharing Results/Integration and Impact

We will submit results to an appropriate academic meeting, such as the Society for Critical Care Medicine and plan to publish the results in a journal targeting critical care medicine, i.e. Journal of Critical Care or Critical Care Medicine. We plan to disseminate results both throughout Regions and

the greater organization. This will include departmental and leadership meetings with the departments participating in this research.

10. References

1. Detterbeck, F.C., et al., *Executive Summary: Diagnosis and management of lung cancer, 3rd ed: American College of Chest Physicians evidence-based clinical practice guidelines*. Chest, 2013. **143**(5 Suppl): p. 7S-37S.
2. Wahidi, M.M., et al., *Technical Aspects of Endobronchial Ultrasound-Guided Transbronchial Needle Aspiration: CHEST Guideline and Expert Panel Report*. Chest, 2016. **149**(3): p. 816-35.
3. Hsu, L.H., et al., *Comparison of 19-gauge eXcelon and WANG MW-319 transbronchial aspiration needles*. Thorac Cancer, 2016. **7**(2): p. 264-70.
4. Biswas, A., et al., *Comparison of the yield of 19-G eXcelon core needle to a 21-G EBUS needle during endobronchial ultrasound guided transbronchial needle aspiration of mediastinal lymph nodes for the detection of granulomas in cases of suspected sarcoidosis*. J Thorac Dis, 2017. **9**(9): p. E864-E866.

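### Should the plan add an equal-pass check in case unblinded operators stop more readily after one needle than the other?

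*Combined protocol and SAP*

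**What the plan says.** Section 4.d describes the allocation: "The randomization aspect of this study involves randomizing which needle size the physician starts with, with subsequent passes alternating between the two needle sizes". Assignments are held by patient: "The randomization assignments for each study ID number will be kept in a document accessible by all investigators for use during enrollments". The same section says investigators are not blinded to the assignment.

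On the number of passes, Section 4.a says "for the study a minimum of 3 passes with each needle will be requested" and leaves further alternating passes to the clinician. Section 4.d describes routine practice as at least four passes, "sometimes more depending on the adequacy of the tissue being obtained", and adds: "Participation in the study will likely result in an additional 1 to 2 total passes per patient".

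The primary outcome in Section 2 is "19-gauge needle yield vs 21-gauge needle yield (true positive + true negative)/total". The variable table in Section 4.e has the row "Total sample yield 19-g | In-person CRF | Outcome | Continuous" and a matching row for the 21-g needle. Passes with each needle are listed there as covariates, and Section 4.c.iv says they are recorded after each procedure.

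Section 4.f plans paired comparisons by gauge, with the test chosen to suit each variable, and a mixed model if more flexibility is needed. Section 4.h lists as a limitation that "procedural variation depends on physician judgment, which could bias results if judgment is differential with respect to needle gauge and/or yield".

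**The concern.** Randomising which needle starts does not randomise which needle finishes. An operator who can see the gauge and decides when to stop could, even unconsciously, stop more readily after a pass with one of the needles. That needle would then more often have the extra pass at nodes with an odd total. If a node counts as a success once any pass with that needle is diagnostic, the extra pass raises that needle's yield. The test is one-sided in favour of the 19-g needle, so a tilt that way would inflate the false-positive rate.

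The protocol names this risk itself, but the SAP has no comparison restricted to equal passes and no stated report of which needle had the extra one. The starting needle is not in the variable table. Section 5 has data entered per patient, and no passage says pass counts are kept per node when a patient has several. If none of this were captured, the named limitation could not be examined afterwards.

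**Working it through.** **1. The plan's own figure.** Section 4.g: 85 pairs (50 × 1.7), SD 10 points, one-sided 5%, 80% power. Detectable difference = (1.645 + 0.842) × 10 / √85 = 2.70 points, which matches the stated 2.7. The concern does not affect this figure.

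**2. How many passes beyond six?** Section 4.d gives an average of 5.5 per node plus 1 to 2 per patient, over 1.7 nodes:

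- (1.7 × 5.5 + 1) / 1.7 = 6.09
- (1.7 × 5.5 + 2) / 1.7 = 6.68

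The mean excess over six is therefore 0.09 to 0.68. With Section 4.a's average of 5, the totals are 5.59 and 6.18, an excess of 0 to 0.18.

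**3. What one extra pass can be worth.** The documents give no per-pass yield, so assume 83% is reached at three passes and score a node as positive if any pass is. With independent passes the per-pass success is 1 − 0.17^(1/3) = 0.446, and the yield at four passes is 1 − 0.17^(4/3) = 90.6%, a gain of 7.6 points. With within-node correlation 0.3 the gain is 4.3 points, and with 0.5 it is 2.9.

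Bias = gain × net share of nodes where the 19-g needle had the extra pass. Suppose every node stopped right after a 19-g pass, at six or seven. Nodes starting with 21-g stop at six and those starting with 19-g go to seven, so the net share is 50% and the bias is 7.6 × 0.5 = 3.8 points (2.2 with correlation 0.3). With gauge-neutral stopping it is zero.

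**4. Stopping that depends on gauge only.** Model: equal needles, random start, six passes, then a stop probability after each pass that differs by gauge, cap 12. Setting A has independent passes and something to detect in every node. Setting B has correlation 0.4 and half the nodes truly negative. The stop odds ratios (after a 19-g versus a 21-g pass) are assumed.

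| Mean extra passes | Odds ratios | Bias A (points) | Bias B (points) |
|---|---|---|---|
| 0.68 | 2.25 / 5.4 / 16 | 0.8 / 1.6 / 2.4 | 0.3 / 0.5 / 0.8 |
| 0.18 | same | 0.4 / 0.7 / 1.1 | 0.1 / 0.2 / 0.3 |
| 0.09 | same | 0.2 / 0.4 / 0.6 | 0.07 / 0.14 / 0.18 |

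Setting B reaches 83% overall with 66% sensitivity in positive nodes (0.5 + 0.5 × 0.66 = 0.83). If 83% is instead the sensitivity in positive nodes, the 0.68 row for B falls to 0.2 / 0.4 / 0.6. If 83% is reached at 5.5 passes instead of three, the largest of these scenarios gives 3.4 points.

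**5. Effect on the test.** At 0.68 extra passes, with 85 nodes and clustering ignored, a one-sided 5% McNemar test rejects a true null as follows.

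| Test | A | B |
|---|---|---|
| Uncorrected | 6.5 / 8.8 / 11.3% | 6.0 / 6.9 / 8.0% |
| Exact | 4.4 / 6.1 / 8.1% | 2.6 / 3.0 / 3.7% |

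**6. Stopping that depends on result, or on both.** If operators continue past six only while both needles are negative, a rule that treats the gauges alike, the null bias is zero to within simulation error (−0.01 and +0.03 points). If they continue only while the 19-g needle is negative, up to 12 passes, the bias is 12.7 points with independent passes and 6.6 with correlation 0.3. In the 12.7-point case mean pass counts differ by only 0.07 per node between needles.

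**7. What is already captured.** Passes per needle are recorded, so their difference shows the net extra passes by gauge. For a single-node patient it identifies directly which needle had the extra pass. The starting needle is held by study ID.

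**The case for a change.** The strongest case for a change is that the protocol names the bias and then leaves it unexamined. A comparison of the first three passes per needle would be free of the shift whenever every node reaches three. It costs almost no power in the scenarios run (37% versus 36% for all passes in setting A, 65% versus 65% in B, at true yields of 83% and 90%). Adjusting for pass count in the mixed model is no substitute, because the count is itself a result of the stopping decision. Stopping on both gauge and result can produce a bias larger than the 7-point hypothesis.

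Part of this stands. No equal-pass analysis is planned, and counts per node in patients with several nodes are not assured. The rest does not carry the case for a change:

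- The large figures come from invented stopping rules. The only driver of extra passes that the documents state is tissue adequacy, which is a result and not a gauge.
- The cost is more than two sentences. Later-pass material would have to be kept and read separately by node and needle, whereas Section 7 has samples identified by standard hospital procedure and Section 4.e lists yield as a total per needle.
- A report of odd-total nodes would probably miss the most damaging pattern, given the 0.07-pass difference. A truly better needle also produces some excess under a common result-based rule.
- A starting-needle term leaves the bias unchanged and does not improve precision (standard error 5.40 versus 5.42 points in setting A, 3.53 versus 3.55 in B).

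**Conclusion.** No change to the plan is needed. If alternation is followed, counts at a node differ by at most one pass, and the random start balances that difference unless stopping depends on gauge. Followed as written, the plan gives a sound paired comparison on this point. The bias requires operator behaviour that the documents do not show and cumulative scoring of yield that they do not fix. If yield is the share of successful passes and stopping ignores results, the bias is essentially nil. How yield is defined is a separate and more basic question.

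The sizes are all assumed scenarios: zero under neutral or common result-based stopping, about 0.1 to 2.4 points under stopping on gauge alone with 83% reached at three passes, and up to about 12.7 under one rule combining gauge and result. No maximum can be stated.

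The reporting gap is one that an analyst fills sensibly: pass counts by needle are collected and fall naturally under the SAP's paired comparisons by gauge. A first-three-pass comparison is a reasonable supportive analysis if pathology can keep the material separable within routine handling. It would leave the primary analysis as it is, so its absence is a fair trade-off, openly disclosed in Section 4.h.

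### The randomised starting needle is neither a listed variable nor a term in the gauge comparison, so any order effect adds chance imbalance and avoidable noise

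*Combined protocol and SAP*

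**What the plan says.** Section 4.a makes each node its own comparison: "For each lymph node sampled, we will alternate between the 19-g and the 21-g with each pass". It asks for at least three passes per needle and adds that "The choice of needle for the first pass will be randomized". Section 4.d confirms that nothing else is randomised: "The randomization aspect of this study involves randomizing which needle size the physician starts with, with subsequent passes alternating between the two needle sizes". On method it says only that "Initial needle size will be randomized using research randomizer", with no ratio, blocking or stratification. On the level of assignment it says that "The randomization assignments for each study ID number will be kept in a document accessible by all investigators for use during enrollments". No passage says whether a second node in the same patient is randomised again or keeps the same start.

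The 4.e table lists pass counts for each needle (for example "Passes with 21-g needle | In-person CRF | Covariate | Continuous"), but not the starting needle, the assigned sequence or the pass order. Section 4.f states that "Bivariate comparisons (by needle gauge) will be conducted using McNemar tests, paired t-tests, or alternatives appropriate for paired data" and offers a linear mixed model only if more flexibility is needed. It names no covariates for that model.

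**The concern.** Within a node, one needle enters untouched tissue and takes passes 1, 3 and 5, and the other takes 2, 4 and 6. Section 3 of the protocol itself says that tissue trauma and aspirated blood can affect yield, and earlier passes could plausibly cause both. With an odd total, the starting needle also gets one pass more. The sponsor evidently saw order as a possible influence, since it chose to randomise it.

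The plan then makes no analytic use of the assignment. Two things follow if order matters. A chance excess of nodes started with one needle moves the gauge estimate in that trial. The order effect also sits in the spread of the node differences, where a model term could have removed it. If all of a patient's nodes share a start, a third problem arises: a test that treats 85 nodes as independent uses the wrong standard error.

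**Working it through.** **Inputs from the documents.** 50 patients, 1.7 nodes each, 85 pairs (4.b, 4.g); one-sided alpha 0.05, SD 10%, 80% power, detectable difference 2.7% (4.g); anticipated yields 83% and 90% (4.g).

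**Assumptions.** Simple 50:50 randomisation of patients; 35 patients with two nodes and 15 with one (85 in all); one start per patient; order effect d = 2, 5 or 10 points; residuals independent between nodes. The documents give no order effect, so d is a range and not an estimate.

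**1. The plan's own figure.** (1.645 + 0.842) × 10/√85 = 2.70 points. The stated 2.7% reproduces.

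**2. Model.** Node difference (19-g minus 21-g) = D + s·d + e, with s = +1 if the 19-g starts and −1 if the 21-g starts. With f the share of nodes started with the 19-g, the unadjusted mean estimates D + (2f−1)d. Since 2f−1 averages zero under 50:50 randomisation, there is no systematic bias. In 20,000 simulated trials per setting, the mean estimate was 2.68 to 2.70 for D = 2.7 and 7.00 to 7.02 for D = 7, at every d from 0 to 10.

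**3. Chance imbalance.** The 95% range for 19-g-first patients is 18 to 32 of 50, and a patient split of 30:20 or worse has probability 0.20. At a 60:40 node split, 2f−1 = 0.2 and the error is 0.2d: 0.4, 1.0 and 2.0 points for d = 2, 5 and 10.

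**4. How the level of assignment matters.** SD(2f−1) = √(Σm²)/85, with m the nodes per patient.
- One start per patient, 35 × 2 and 15 × 1 nodes: Σm² = 155, SD 0.146.
- One start per patient, 1/2/3 nodes in 45/40/15% (also mean 1.7): Σm² = 170, SD 0.153.
- Independent start for each node: 1/√85 = 0.108.
- Start switched between a patient's nodes, 45/40/15% mix: only the 30 patients with an odd number of nodes contribute, so √30/85 = 0.064.

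**5. Precision and validity of the unadjusted paired t-test.** The true variance of the mean is 100/85 + d² × 155/85². The test's own variance is about (100 + d²)/85, because it ignores the shared start.

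| d | True SE | SE used by the test | Type I error, formula | Type I error, simulated | Power at 2.7, simulated |
|---|---|---|---|---|---|
| 2 | 1.12 | 1.11 | 0.053 | 0.055 | 0.78 |
| 5 | 1.31 | 1.21 | 0.064 | 0.063 | 0.70 |
| 10 | 1.82 | 1.53 | 0.083 | 0.084 | 0.53 |

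The formula column is the upper normal tail at 1.645 × (SE used ÷ true SE). For d = 5 this is 1.645 × 0.927 = 1.52, tail 0.064.

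**6. With a starting-needle term.** The SE stays at 1.09 to 1.10, type I error at 0.050 to 0.054 and power at 2.7 points at 0.78 to 0.79 for every d tested.

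**7. Balancing the list alone is not enough.** With exactly 25:25 patients and no term (5,000 simulated trials per setting), type I error falls to 0.033 and 0.014 for d = 5 and 10. Power at 2.7 points is 0.73 and 0.55.

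**8. At the planned difference.** With D = 7 and SD 10%, power is 0.99 or more at every d, adjusted or not.

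**9. If yield is scored correct or not for each node.** Yields of 83% and 90% need at least 7% discordant pairs, so the SD of the differences is at least √(0.07 − 0.0049) = 25.5 points (variance 651). The detectable difference is then 2.4865 × √(651/85) = 6.88. Removing d = 5 gives 2.4865 × √(626/85) = 6.75, a gain of about 2%. The formula in step 5 with 651 in place of 100 gives type I error of 0.053 at d = 5 and 0.059 at d = 10.

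**The case against.** The best reply is that the design already deals with order. The start is randomised and needles alternate, so over six passes the mean pass position is 3.0 for the starter and 4.0 for the other, which should keep d small. No value of d has a source; at d = 2 the SE is 1.12 against 1.09. The hypothesis concerns 7 points, where power hardly moves on the stated SD. The assignment list is kept and 4.f permits a mixed model with covariates, so adjustment is possible. The enrolment checklist and CRF mentioned in Section 5 are not shown and may record the start.

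Most of this stands as a limit on size. It does not remove the point: the list gives the assigned start and not necessarily the actual one, and a conditional model with unnamed covariates leaves the choice until after the data are seen.

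Three stronger readings are not supported:
- A reader might infer that the needle comparison is biased. Step 2 shows that it is not, unless allocation were unequal or the open list were not followed, and the documents show neither.
- A reader might say that the randomised factor is never used. It sets the sequence in every patient; what is missing is its use in the analysis.
- A reader might expect adjustment to cut the detectable difference from 2.70 to 2.34 points. That needs d = 5 and a 10% SD that already contains it: 2.4865 × √(75/85) = 2.34. The documents support neither condition, and step 9 shows how little is gained with a binary yield.

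**Conclusion.** The point holds as one of efficiency, test validity and clarity. The starting needle is the only randomised factor, is absent from 4.e and has no specified term in 4.f. The consequence is an error of (2f−1)d in any one trial and avoidable noise. If nodes within a patient share a start and the list is unblocked, the node-level t-test is also mildly anti-conservative. On the plan's 10% SD the loss is small near d = 2, material from about d = 5 at the 2.7-point target, and negligible for power at 7 points. That SD is unsupported in the documents and looks low for a binary node result; a larger SD shrinks the relative effect of order. One start per patient is the natural reading of a list indexed by study ID, but it is an inference.

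**What to change.** 1. Record the starting needle actually used for each node on the CRF, and list it in 4.e beside the pass counts. Keep the assigned start as well.
2. In 4.f, pre-specify the primary gauge model as the node-level 19-g minus 21-g difference regressed on starting needle (+1/−1), with the intercept as the gauge effect and patient clustering in the standard error or as a random effect. A plain node-level regression without clustering is not enough. If yield is binary for each node, use a paired test stratified by starting needle that also allows for clustering.
3. State in 4.d how the start is set for a patient's second and later nodes.

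Optional refinements are to switch the start between a patient's nodes and to generate the list in balanced blocks. By step 7, balancing does not replace the model term.

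The cost is one CRF field, one degree of freedom and a few sentences of text, with no extra patients or passes.
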